Protocol CV43043 has been amended to address the feedback and questions received as part of a multinational clinical trial authorization application process. Changes to the protocol, along with a rationale for each change, are summarized below:

- Updates have been made to the Study Rationale and Benefit-Risk Assessment section to reflect recent developments in coronavirus diseases 2019 (COVID-19) treatment (Section 1.3).
- Two new secondary efficacy endpoints have been added to evaluate maintenance of symptom alleviation or improvement out to 43 hours (48 hours \pm 10% to allow for variability in the timing of completion of patient reported outcomes by patients) (Sections 2 and 6.4.2).
- New exploratory endpoint has been added to include optional exit interviews in order to establish supportive evidence for the COVID-19 Symptom Diary (Sections 2, 3.3.5 and 6.4.5; Appendix 1).
- The number of sites where the study will be conducted has been updated (Sections 3.1 and 9.5).
- Adolescent enrollment numbers were clarified as approximately 100 adolescent patients to match text in Sections 3.1 and 4.2 (Section 3.3.2).
- Web links to CDC adolescent growth charts were added. These were previously erroneously omitted (Section 3.3.2).
- The exclusion criterion and prohibited therapy related to prior use of amiodarone and hydroxychloroquine has been modified to exclude use within 3 months prior to screening due to the long and variable half-life of both drugs, to further mitigate any potential for drug-drug interaction with RO7496998 (AT-527) (Sections 4.1.2 and 4.4.3).
- The exclusion criterion related to prior treatment with an investigational drug has been modified to exclude use within 3 months prior to screening (Section 4.1.2).
- The exclusion criteria related to prior treatment with a COVID-19 therapeutic has been expanded and clarified to provide more examples and in response to a changing therapeutic landscape and questions from participating sites (Section 4.1.2).
- The units were standardized for the WBC, ANC, and platelet counts in the exclusion criteria (Section 4.1.2).
- It has been clarified that patients with stable chronic viral infections are eligible to participate in the study, providing other eligibility criteria are met (Section 4.1.2).

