- Abnormal laboratory test results at screening, defined as meeting any of the following sets of criteria:
 - ALT or AST > 5 × upper limit of normal (ULN)
 - Total bilirubin > 1.5 × ULN, unless the patient has known Gilbert disease
 - Creatinine clearance < 60 mL/min
 - Total WBC < 2,500/mm³ or ANC < 800/mm³
 - Platelet count < 80/mm³

Local laboratory test results from standard-of-care tests performed prior to obtaining written informed consent and ≤ 48 hours before randomization may be used; such tests do not need to be repeated for screening.

- Requirement of any prohibited medications during the study
- *Other known active viral or bacterial infection at the time of screening, such as influenza*
Note: This exclusion does not apply to patients with stable chronic viral infections, such as chronic HCV or HIV providing other eligibility criteria are met.
- Any clinically significant medical condition or laboratory abnormality that, in the opinion of the investigator, could jeopardize the safety of the patient or affect patient compliance or safety/efficacy observations during the study
- *COVID-19 vaccination within ≤40-days prior to enrollment (second dose if applicable)*

End of Study

The end of this study is defined as the date when the last patient, last visit (i.e., safety follow-up telephone call), occurs or the date at which the last data point required for statistical analysis or safety follow-up is received from the last patient, whichever occurs later. The end of the study is expected to occur approximately 33 days after the last patient has been enrolled.

In addition, the Sponsor may decide to terminate the study at any time.

Length of Study

The total length of the study, from screening of the first patient to the end of the study, is expected to be approximately 6 months.

Investigational Medicinal Products

The investigational medicinal product for this study is RO7496998 (AT-527) or matching placebo.

Test Product (Investigational Drug)

For patients randomized to receive study drug, RO7496998 (AT-527) will be provided as 275 mg tablets; two tablets will be administered orally BID from Day 1 to Day 5.

Comparator

For patients randomized to receive placebo, placebo will be provided as 275 mg tablets; two tablets will be administered orally BID from Day 1 to Day 5.

Statistical Methods

Primary Analysis

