4.1.2 Exclusion Criteria

Patients who meet any of the following criteria will be excluded from study entry:

- Clinical signs indicative of COVID-19 illness requiring hospitalization defined as any of the following:
 - In adults: respiratory rate \geq 30, heart rate \geq 125 bpm, SpO₂ \leq 93% on room air
 - In adolescents: respiratory rate \geq 30, heart rate \geq 130 bpm, SpO₂ \leq 93% on room air
- Admitted to a hospital prior to randomization or is hospitalized (inpatient) at randomization due to COVID-19

Note: If local policy requires COVID-19 isolation or internment in a hospital or similar facility, such as in Japan, but those patients otherwise meet the inclusion criteria, this exclusion may not apply.

- In the opinion of the investigator, is likely to experience imminent deterioration and require hospitalization
- Treatment with an investigational drug within 5 half-lives or 3 months (whichever is longer) of randomization
- Treatment with a COVID-19 therapeutic agent including, but not limited to, other direct or indirect acting antivirals *against SARS-CoV-2 (such as remdesivir or favipiravir), systemic or inhaled steroids (such as dexamethasone or inhaled budesonide), colchicine, ivermectin, interferons, convalescent plasma, monoclonal antibodies against SARS CoV-2 or interleukin 6 (IL-6), intravenous immunoglobulin or other EUA-approved treatments within 3 months or less than 5 drug elimination half-lives (whichever is longer) prior to the screening visit*
- Concomitant use of P-glycoprotein (P-gp) inhibitors or inducers listed in Section 4.4.3
- Known allergy or hypersensitivity to components of study drug
- Pregnant or breastfeeding, or intending to become pregnant during the study or within 30 days after the final dose of RO7496998 (AT-527)

Women of childbearing potential must have a negative pregnancy test result at screening prior to initiation of study drug.

- Abnormal laboratory test results at screening, defined as meeting any of the following sets of criteria:
 - ALT or AST $>5 \times$ upper limit of normal (ULN)
 - Total bilirubin $>1.5 \times$ ULN, unless the patient has known Gilbert disease
 - Creatinine clearance $<60 \text{ mL/min}$
 - Total WBC $<2,500/\text{mm}^3$ or ANC $<800/\text{mm}^3$
 - Platelet count $<80/\text{mm}^3$

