Local laboratory test results from standard-of-care tests performed prior to obtaining written informed consent and ≤ 48 hours before randomization may be used; such tests do not need to be repeated for screening

- Requirement of any prohibited medications during the study
- *Other known active viral or bacterial infection at the time of screening, such as influenza*

Note: This exclusion does not apply to patients with stable chronic viral infections, such as chronic HCV or HIV providing other eligibility criteria are met.

- Any clinically significant medical condition or laboratory abnormality that, in the opinion of the investigator, could jeopardize the safety of the patient or affect patient compliance or safety/efficacy observations during the study
- *COVID-19 vaccination within ≤ 40 -days prior to enrollment (second dose if applicable); see Section 4.5.2 for documentation requirements pertaining to vaccine type and date of dosing*

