4.5.1 Informed Consent Forms and Screening Log

Written informed consent/assent (where appropriate) for participation in the study must be obtained before performing any study-related procedures (including screening evaluations).

Informed Consent Forms (and Assent Forms where appropriate) for enrolled patients and for patients who are not subsequently enrolled will be maintained at the study site.

All screening evaluations must be completed and reviewed to confirm that patients meet all eligibility criteria before enrollment. Screened patients and screen failures will be tracked in IxRS.

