4.5.5 Laboratory, Biomarker, and Other Biological Samples

Samples for the following laboratory tests will be sent to the study site's local laboratory for analysis. Collection of hematology, chemistry, coagulation and pregnancy laboratory samples will be performed locally as per schedule of activities. Historical standard-of-care laboratory tests performed locally, prior to obtaining written informed consent, may be used as the screening labs as indicated below; such tests do not need to be repeated for screening. If standard-of-care laboratory tests are conducted prior to obtaining written informed consent, documentation of results must be available.

Blood sample collection may be performed by a MN professional.

- Hematology: WBC count, RBC count, hemoglobin, hematocrit, platelet count, and differential count (neutrophils, eosinophils, basophils, monocytes, lymphocytes, other cells). If using a historical standard-of-care test, it must be performed \leq 48 hours prior to randomization.
- Chemistry panel (serum or plasma): bicarbonate or total carbon dioxide (if considered standard of care for the region), sodium, potassium, chloride, glucose, BUN or urea, creatinine, total protein, albumin, phosphate, calcium, total and direct bilirubin, ALP, ALT, AST, triglycerides, CK, CRP, ferritin, cholesterol, amylase, lipase, urate, procalcitonin, and LDH. If using a historical standard-of-care test, it must be performed \leq 48 hours prior to randomization.
- Pregnancy test

All women of childbearing potential will have a pregnancy test at screening. This will be a urine or serum test depending on local guidelines. If a historical serum test is conducted, it must be performed \leq 48 hours prior to randomization.

- SARS-CoV-2 approved diagnostic test (RT-PCR or validated rapid antigen test) for screening by an NP swab. If using a historical test, it must be performed \leq 72 hours prior to randomization.
- Coagulation: INR, aPTT, PT, D-dimer, and fibrinogen. If using a historical standard-of-care test, it must be performed \leq 48 hours prior to randomization.

Samples for the following laboratory tests will be sent to designated central laboratories or the Sponsor or a designee for analysis:

- Plasma samples for PK analysis
- Serum samples for SARS-CoV-2 antibody titer and virology tests
- NP or nasal swabs and saliva samples for SARS-CoV-2 virology tests
- NP or nasal swabs for respiratory pathogen co-infections panel (multiplex BioFire® assay)

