Appendix 1: Schedule of Activities

- Safety samples (hematology, chemistry and coagulation) will be analyzed locally. Refer to Section 4.5.5 for information regarding the acceptability of historical standard-of-care tests.
- Chemistry panel (serum or plasma): bicarbonate or total carbon dioxide (if considered standard of care for the region), sodium, potassium, chloride, glucose, BUN or urea, creatinine, total protein, albumin, phosphate, calcium, total and direct bilirubin, ALP, ALT, AST, triglycerides, CK, CRP, ferritin, cholesterol, amylase, lipase, urate, procalcitonin, and LDH.
- All women of childbearing potential will have a pregnancy test at screening. This will be performed locally and will be a urine or serum test, depending on local guidelines. Refer to Section 4.5.5 for information regarding the acceptability of historical standard-of-care tests.
- Performed at or prior to Screening, nasopharyngeal swabs will be analyzed for the SARS-CoV-2 by approved diagnostic test (RT-PCR or validated rapid antigen test) locally.
- Swab samples and saliva samples should be collected at approximately the same time every day where possible. The sample on Day 1 should be collected **prior to dosing**. At least two nasopharyngeal swabs, one from each nostril, will be taken at each visit. Should the patient decline a nasopharyngeal swab, a nasal swab from each nostril may be collected instead.
- For saliva sample at Day 2 only: patients can take the sample at home and bring to site on Day 3 (if they are having on-site visits) or the mobile nurse/physician can pick the sample up at Day 3 (if they have consented to home visits).
- Optional samples collected in adult patients only and who have consented to PK and biomarker intensive sampling.
- A plasma sample will be generated from the blood sample obtained following PBMC processing and will be stored for biomarker research. No additional blood draw is needed. Samples for PBMC may not be collected at some timepoints if sample stability requirements for processing will not be met. Please refer to the laboratory manual for more details.
- At Day 1, Day 5, Day 14 and ET, Nasosorption sample to be taken after the nasopharyngeal swabs.

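### The platelet exclusion limit is printed as below 80/mm³, probably 1,000 times too low, so the criterion excludes practically no one

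*Protocol*

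**What the plan says.** The laboratory exclusions in the Protocol Synopsis include "Platelet count < 80/mm³". Section 4.1.2 gives the same number in the same unit. The neighbouring line in both lists reads "Total WBC < 2,500/mm³ or ANC < 800/mm³", so all three blood-count limits are absolute counts per mm³.

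The amendment summary at the front of the protocol reports, for Section 4.1.2: "The units were standardized for the WBC, ANC, and platelet counts in the exclusion criteria". Neither the protocol nor the SAP gives any other numeric platelet limit for eligibility.

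Three other provisions bear on the point:
- Platelet count is measured at screening. Section 4.5.5 lists "Hematology: WBC count, RBC count, hemoglobin, hematocrit, platelet count, and differential count", and Section 4.5.1 requires that "All screening evaluations must be completed and reviewed to confirm that patients meet all eligibility criteria before enrollment".
- Section 4.1.2 also excludes "Any clinically significant medical condition or laboratory abnormality that, in the opinion of the investigator, could jeopardize the safety of the patient".
- The Appendix 1 footnotes state that "Safety samples (hematology, chemistry and coagulation) will be analyzed locally", and Section 3.1 plans about 220 sites.

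**The concern.** A limit of 80 platelets per mm³ is far below anything expected in a stable outpatient, so as a numeric rule it screens out practically nobody. Section 5.1 says that the eligibility criteria are meant to keep out patients at higher risk of toxicity. For platelets, the printed number does not do that.

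Three things are at stake:
- **Uniformity.** With no usable limit, the decision on a low count passes to individual judgment, on local laboratory results, at about 220 sites. If some sites read the figure as thousands and others apply it literally, eligibility differs by site.
- **Deviation reporting.** Section 9.2 does not allow eligibility criteria to be waived, so the written number is the rule. A patient at 40,000/mm³ complies with it and would not appear in the eligibility-deviation summary planned in Section 6.2.
- **Safety in the patients admitted.** The protocol accepts chronic liver disease as a risk factor (3.3.2) and stable chronic HCV (4.1.2). It permits low-dose aspirin (4.4.1), and it names warfarin, apixaban and rivaroxaban as drugs to manage with caution or staggered dosing rather than to prohibit (4.4.2). That a low platelet count adds bleeding risk in such patients is a clinical inference; the protocol does not say so.

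**Working it through.** The limit is a printed threshold, not a derived figure, so there is no formula of the plan's to reproduce. The check is a unit conversion and a comparison of sizes.

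**Inputs from the protocol (Synopsis and Section 4.1.2):** platelets 80/mm³, ANC 800/mm³, WBC 2,500/mm³.

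**Assumptions, not in the documents:** a usual platelet count of 150,000 to 450,000/mm³; 10,000/mm³ as an example of severe thrombocytopenia; 80,000/mm³ as the intended limit.

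**Step 1: common unit.** 1 mm³ = 1 µL and 1 L = 10⁶ µL, so the count per mm³ × 10⁶ ÷ 10⁹ gives the value in 10⁹/L.

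| Limit | Per mm³ | × 10⁹/L |
|---|---|---|
| WBC | 2,500 | 2.5 |
| ANC | 800 | 0.8 |
| Platelets, as printed | 80 | 0.08 |
| Platelets, presumed intent | 80,000 | 80 |

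**Step 2: comparison within the list.** Printed platelets to ANC: 80/800 = 0.10. Printed platelets to WBC: 80/2,500 = 0.032. The platelet limit is thus one tenth of the neutrophil limit. With the presumed value the ratios are 80,000/800 = 100 and 80,000/2,500 = 32.

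**Step 3: comparison with a usual count.**
- As printed: 80/150,000 = 0.053% and 80/450,000 = 0.018%.
- Presumed intent: 80,000/150,000 = 53% and 80,000/450,000 = 18%, a workable limit.

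**Step 4: dependence on the assumed range.** 10,000/80 = 125. Even a patient with severe thrombocytopenia is 125 times above the printed limit, so the conclusion does not turn on the exact usual range.

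**Step 5: size of the slip.** 80,000/80 = 1,000. If 80,000/mm³ was meant, counts from 80 to 79,999/mm³ pass a criterion that they should fail.

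**Step 6: is it a stray misprint?** The same figure stands in two separate lists, and the WBC and ANC limits beside it are sensible in the same unit. The amendment note that these units were standardized fits a lost factor of 1,000. That cause is an inference, because the text before the amendment is not available.

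**The case against.** The strongest reply concerns consequence, since the number itself cannot be defended:

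- **Low counts would still be seen.** SAP 5.6.3 tabulates platelets by toxicity grade at baseline and at the worst later value, and lists values outside the reference range. SAP 5.4.4.4 reports platelet values at baseline and Day 5. This is correct: the data are not lost. But those outputs come after enrollment. They do not act as an eligibility check, and they do not mark the patient as a deviation.
- **No platelet risk is described for this drug.** Protocol 1.3 and 5.1.1 report no target-organ toxicity and no pattern of laboratory abnormalities. Treatment lasts 5 days, hematology is repeated at Day 5, and an independent committee evaluates safety. This stands, and it limits the likely harm. Nothing in the documents shows how many outpatients would fall between the two limits; the number may be small or zero. The factor of 1,000 measures the error in the threshold, not its effect on patients.
- **Investigators can still exclude such patients.** This also stands. Screening results must be reviewed, and the discretionary exclusion covers a clinically significant abnormality. It does not replace one objective limit applied alike at every site.
- **Sites may recognise the slip and read thousands.** Possibly, but the documents do not show how sites read it, and a safety threshold should not need guessing.

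**Conclusion.** The concern holds: the limit is wrong as written in the operative eligibility criteria and should be fixed. The printed 80/mm³ is 0.018% to 0.053% of an assumed usual count and excludes practically nobody. If 80,000/mm³ was intended, the limit is 1,000 times too low.

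What is lost is a uniform numeric limit and the ability to identify breaches of it as deviations. Protection through investigator judgment remains, as does later reporting of platelet values.

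The finding rests on two stated assumptions. The usual platelet range is not in the documents, although the conclusion is insensitive to it. The value 80,000/mm³ is presumed and needs the sponsor's confirmation. The number of patients affected is unknown. Sample size, power, type I error and the primary estimand do not depend on this limit.

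**What to change.** 1. The sponsor confirms the intended value, presumably below 80,000/mm³ (80 × 10⁹/L).
2. Correct the line in the Protocol Synopsis and in Section 4.1.2. Printing the limit in both units would help, because the samples are read by local laboratories.
3. Send all sites a clarification that states the value and the unit.
4. If patients have already been enrolled under this wording, check their screening platelet counts against the corrected limit and list any below it.

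The cost is one line in two places, a site letter, and one query on screening data that the protocol already collects. No analysis in the SAP needs to change.

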1.2 BACKGROUND ON RO7496998 (AT-527)

RO7496998 (AT-527) is a phosphoramidate prodrug of a unique 6-modified purine nucleotide prodrug discovered by Atea Pharmaceuticals Inc. In laboratory studies, RO7496998 (AT-527) potently inhibits the RNA-dependent RNA polymerase of several single-stranded RNA viruses. RO7496998 (AT-527) is converted to its active intracellular triphosphate form (AT-9010) through a series of intermediate metabolites. RO7496998 (AT-527) has demonstrated sub-micromolar potency against a range of coronaviruses, including SARS-CoV-1 (90% effective concentration $[EC_{90}] = 0.34 \mu M$) and SARS-CoV-2 (mean $EC_{90} = 0.5 \mu M$). RO7496998 (AT-527), at once daily doses up to 553 mg (free base), has been evaluated in two completed clinical studies in healthy volunteers and patients infected with hepatitis C virus (HCV). In the recently completed Phase II study (AT-01B-002), RO7496998 (AT-527) in patients infected with HCV was well-tolerated for durations of up to 12 weeks and achieved a high rate of antiviral efficacy, with no safety issues.

RO7496998 (AT-527) is administered to patients orally as tablets. In healthy volunteers and patients infected with HCV, RO7496998 (AT-527) exhibited a predictable and predictive pharmacokinetic (PK) and pharmacodynamic (PD) profile associated with the observed antiviral efficacy in patients infected with HCV. This supportive human PK profile is likely to be observed with dosing of patients with COVID-19 and is expected to be sufficient for achieving antiviral efficacy based on the sub-micromolar EC_{90} for the active triphosphate of RO7496998 (AT-527) against SARS-CoV-2 virus replication in laboratory studies.

The safety and efficacy of RO7496998 (AT-527), at doses of 550 mg twice a day (BID), in hospitalized patients age ≥ 18 years with moderate COVID-19 who have risk factors for poor outcome are currently being evaluated in a Phase II study (AT-03A-001). The safety and pharmacokinetics of RO7496998 (AT-527) at doses of 550 mg BID, have also been evaluated in healthy volunteers (AT-03A-002). Summaries from these studies are briefly outlined in the sections below.

AT-03A-002

This ongoing Phase I study AT-03A-002 is a randomized (1:1), double-blind, placebo-controlled study to assess the safety and pharmacokinetics of multiple doses of RO7496998 (AT-527) in healthy subjects. *Subjects* received RO7496998 (AT-527) at doses of 550 mg or matching placebo, BID for 5 days.

Twenty subjects (10 subjects in the active group and 10 subjects in the placebo group) were enrolled and have completed dosing and follow-up through Day 10. No subjects have prematurely discontinued the study drug and no serious adverse events have been reported. All adverse events were mild, limited in duration, and were resolved by the end of the study.

There were no other clinically significant treatment-emergent laboratory abnormalities, ECG abnormalities, or vital sign abnormalities.

AT-03A-001

Phase II study AT-03A-001 is an ongoing randomized (1:1), double-blind, placebo-controlled study to evaluate the safety and efficacy of RO7496998 (AT-527) in adult patients with moderate COVID-19 who are at high risk for poor outcomes. Patients must have either obesity (BMI > 30), hypertension, diabetes, or asthma. The study protocol targets enrollment of 190 patients.

Patients are treated with RO7496998 (AT-527) at doses of 550 mg or matching placebo, BID (approximately every 12 hours) for 5 days (total of 10 doses).

Safety reviews have been performed by a Data Safety Monitoring Board (DSMB) for the first two 20-patient cohorts (40 patients total) with a data cutoff date of 11 December 2020. Data remains blinded in this ongoing study. To date, pertinent events reviewed by the DSMB include:

- Serious adverse events assessed by the investigator as unrelated to study drug were reported in 3 patients: 2 patients experienced decreased oxygen saturation (1 case resulting in death due to COVID-19 pneumonia) and 1 patient experienced acute respiratory failure. Progression of COVID-19 is common in this clinical setting.
- Grade 3 or 4 adverse events of laboratory abnormalities were reported in 2 patients: in 1 patient, one event each of isolated lipase increase and isolated triglycerides increase with no associated symptoms; and in another patient, one event of hyperbilirubinemia (normal ALT/AST).
- Grade 3 and 4 laboratory abnormalities of special interest for nucleosides did not reveal any signals or patterns suggestive of drug toxicity.

Cumulative blinded data review from 40 patients enrolled in the study continues to support a favorable safety profile of RO7496998 (AT-527). The study DSMB recommended the study continue without modification.

Refer to the AT-527 Investigator's Brochure for details on nonclinical and clinical studies.

